7.10 Other Outcomes

Not applicable

7.11 Safety Analysis

7.11.1 Adverse Events

7.11.1.1 Overview of Treatment-Emergent Adverse Events

Analysis Set:Safety Analysis SetAnalysis Variables:TEAE

Categories:	Relationship to Study Drug	[Related, Not Related]		
	Intensity	[Mild, Moderate, Severe]		
Analytical Methods:	The following summaries will be pro	vided by dose.		
	(1) Overview of Treatment-Emerge	ent Adverse Events		
	1) All Treatment-Emergent Adverse Events (number of events, number and percentage of subjects)			
	 2) Relationship of Treatment-Emergent Adverse Events to Study Drug (number of events, number and percentage of subjects) 			
	3) Intensity of Treatment-Emergent Adverse Events (number of events, number and percentage of subjects)			
	 4) Treatment-Emergent Adverse Events Leading to Study Drug Discontinuation (number of events, number and percentage of subjects). 			
	5) Serious Treatment-Emergent Adverse Events (number of events, number and percentage of subjects)			
	6) Relationship of Serious Treatment-Emergent Adverse Events to Study Drug (number of events, number and percentage of subjects)			
	7) Serious Treatment-Emergent Adverse Events Leading to Study Drug Discontinuation (number of events, number and percentage of subjects)			
	8) Treatment-Emergent Adverse Events Resulting in Death (number of events, number			
	and percentage of subjects)			
	I EAEs will be counted according to the rules below.			
	• Summaries for 2) and 6)			
	A subject with occurrences of T be counted once in the Related of	EAE in both categories (ie, Related and Not Related) will category.		
	• Summary for 3)			
	A subject with multiple occurrences of TEAE will be counted once for the TEAE with the maximum intensity.			
	• Summaries other than 2), 3) and 6)			
	A subject with multiple occurrences of TEAE will be counted only once.			
	Number of events			
	For each summary, the total number	of events will be calculated.		
7.11.1.2 Overvi	iew of Treatment-Emergent A	dverse Events Occurred in Single Dose		

Period

Analysis Set:	Safety Analysis Set		
Analysis Variables:	TEAE occurred in single dose period		
Categories:	Relationship to Study Drug	[Related, Not Related]	
	Intensity	[Mild, Moderate, Severe]	
Analytical Methods:	The following summaries will be prov	vided by dose.	
	(1) Overview of Treatment-Emergent Adverse Events		

1) All Treatment-Emergent Adverse Events (number of events, number and percentage of

subjects)

- 2) Relationship of Treatment-Emergent Adverse Events to Study Drug (number of events, number and percentage of subjects)
- 3) Intensity of Treatment-Emergent Adverse Events (number of events, number and percentage of subjects)
- 4) Serious Treatment-Emergent Adverse Events (number of events, number and percentage of subjects)
- 5) Relationship of Serious Treatment-Emergent Adverse Events to Study Drug (number of events, number and percentage of subjects)
- 6) Serious Treatment-Emergent Adverse Events Leading to Study Drug Discontinuation (number of events, number and percentage of subjects)
- 7) Treatment-Emergent Adverse Events Resulting in Death (number of events, number and percentage of subjects)

TEAEs will be counted according to the rules below.

Number of subjects

- Summaries for 2) and 5)A subject with occurrences of TEAE in both categories (ie, Related and Not Related) will be counted once in the Related category.
- Summary for 3)
 A subject with multiple occurrences of TEAE will be counted once for the TEAE with the maximum intensity.
- Summaries other than 2), 3) and 5)
- A subject with multiple occurrences of TEAE will be counted only once.

```
Number of events
```

For each summary, the total number of events will be calculated.

7.11.1.3 Overview of Treatment-Emergent Adverse Events Occurred in Multiple Dose Period

Analysis Set:	Safety Analysis Set		
Analysis Variables:	TEAE occurred in multiple dose p	eriod	
Categories:	Relationship to Study Drug	[Related, Not Related]	
	Intensity	[Mild, Moderate, Severe]	
Analytical Methods:	The following summaries will be p	provided by dose.	
	(1) Overview of Treatment-Eme	rgent Adverse Events	
	 All Treatment-Emergent Adverse Events (number of events, number and percenta subjects) 		
 Relationship of Treatment-Emergent Adverse Events to Study Drug (number of number and percentage of subjects) 			
	 Intensity of Treatment-Emergent Adverse Events (number of events, number and percentage of subjects) 		
	4) Treatment-Emergent Adver	se Events Leading to Study Drug Discontinuation (number	

of events, number and percentage of subjects)

- 5) Serious Treatment-Emergent Adverse Events (number of events, number and percentage of subjects)
- 6) Relationship of Serious Treatment-Emergent Adverse Events to Study Drug (number of events, number and percentage of subjects)
- 7) Serious Treatment-Emergent Adverse Events Leading to Study Drug Discontinuation (number of events, number and percentage of subjects)
- 8) Treatment-Emergent Adverse Events Resulting in Death (number of events, number and percentage of subjects)

TEAEs will be counted according to the rules below.

Number of subjects

- Summaries for 2) and 6)
 A subject with occurrences of TEAE in both categories (ie, Related and Not Related) will be counted once in the Related category.
- Summary for 3) A subject with multiple occurrences of TEAE will be counted once for the TEAE with the maximum intensity.
- Summaries other than 2), 3) and 6)
 - A subject with multiple occurrences of TEAE will be counted only once.

For each summary, the total number of events will be calculated.

7.11.1.4 Displays of Treatment-Emergent Adverse Events

Analysis Set:	Safety Analysis Set			
Analysis Variables:	TEAE			
Categories:	Intensity [Mild, Moderate, Severe]			
Analytical Methods:	The following summaries will be provided using frequency distribution by dose.			
	TEAEs will be coded using the MedDRA and will be summarized using SOC and PT. SOC			
	will be sorted alphabetically and PT will be sorted in decreasing frequency for tables provided			
	by SOC and PT. SOC and PT will be sorted in decreasing frequency for tables provided by			
	SOC only or PT only.			
	(1) Treatment-Emergent Adverse Events by System Organ Class and Preferred Term			
	(2) Treatment-Emergent Adverse Events by System Organ Class			
	(3) Treatment-Emergent Adverse Events by Preferred Term			
	(4) Drug-Related Treatment-Emergent Adverse Events by System Organ Class and Preferred Term			
	(5) Intensity of Treatment-Emergent Adverse Events by System Organ Class and Preferred			
	Term			
	(6) Intensity of Drug-Related Treatment-Emergent Adverse Events by System Organ Class, and Preferred Term			
	CONFIDENTIAL			

Number of events

- (7) Treatment-Emergent Adverse Events Leading to Study Drug Discontinuation by System Organ Class and Preferred Term
- (8) Serious Treatment-Emergent Adverse Events by System Organ Class and Preferred Term
- (9) QTc prolongation associated Treatment-Emergent Adverse Events by System Organ Class and Preferred Term
- (10) Neurologic Treatment-Emergent Adverse Events by System Organ Class and Preferred Term
- (11) Hyperprolactinemia associated Treatment-Emergent Adverse Events by System Organ Class and Preferred Term
- (12) Drug-Related QTc prolongation associated Treatment-Emergent Adverse Events by System Organ Class and Preferred Term
- (13) Drug-Related Neurologic Treatment-Emergent Adverse Events by System Organ Class and Preferred Term
- (14) Drug-Related Hyperprolactinemia associated Treatment-Emergent Adverse Events by System Organ Class and Preferred Term

The frequency distribution will be provided according to the rules below. Number of subjects

- Summary tables other than (5), and (6) A subject with multiple occurrences of TEAE within a SOC will be counted only once in that SOC. A subject with multiple occurrences of TEAE within a PT will be counted only once in that PT. Percentages will be based on the number of subjects in the safety analysis set.
- Summary tables for (5) and (6) A subject with multiple occurrences of TEAE within a SOC or a PT will be counted only once for the TEAE with the maximum intensity. Percentages will be based on the number of subjects in the safety analysis set.

7.11.1.5 Displays of Treatment-Emergent Adverse Events Occurred in Single Dose Period

Analysis Set:	Safety Analysis Set				
Analysis Variables:	TEAE occurred in single of	lose period			
Categories:	Intensity	[Mild, Moderate, Severe]			
Analytical Methods:	The following summaries	will be provided using frequency distribution by dose.			
	TEAEs will be coded usin	g the MedDRA and will be summarized using SOC and PT. SOC			
	will be sorted alphabetical	ly and PT will be sorted in decreasing frequency for tables provided			
	by SOC and PT. SOC and PT will be sorted in decreasing frequency for tables provided by				
	SOC only or PT only.				
	(1) Treatment-Emergent A	dverse Events by System Organ Class and Preferred Term			
	(2) Treatment-Emergent A	dverse Events by System Organ Class			
	(3) Treatment-Emergent A	dverse Events by Preferred Term			

- (4) Drug-Related Treatment-Emergent Adverse Events by System Organ Class and Preferred Term
- (5) Intensity of Treatment-Emergent Adverse Events by System Organ Class and Preferred Term
- (6) Intensity of Drug-Related Treatment-Emergent Adverse Events by System Organ Class, and Preferred Term
- (7) Serious Treatment-Emergent Adverse Events by System Organ Class and Preferred Term
- (8) QTc prolongation associated Treatment-Emergent Adverse Events by System Organ Class and Preferred Term
- (9) Neurologic Treatment-Emergent Adverse Events by System Organ Class and Preferred Term
- (10) Hyperprolactinemia associated Treatment-Emergent Adverse Events by System Organ Class and Preferred Term
- (11) Drug-Related QTc prolongation associated Treatment-Emergent Adverse Events by System Organ Class and Preferred Term
- (12) Drug-Related Neurologic Treatment-Emergent Adverse Events by System Organ Class and Preferred Term
- (13) Drug-Related Hyperprolactinemia associated Treatment-Emergent Adverse Events by System Organ Class and Preferred Term

The frequency distribution will be provided according to the rules below. Number of subjects

- Summary tables other than (5), and (6) A subject with multiple occurrences of TEAE within a SOC will be counted only once in that SOC. A subject with multiple occurrences of TEAE within a PT will be counted only once in that PT. Percentages will be based on the number of subjects in the safety analysis set.
- Summary tables for (5) and (6) A subject with multiple occurrences of TEAE within a SOC or a PT will be counted only once for the TEAE with the maximum intensity. Percentages will be based on the number of subjects in the safety analysis set.

7.11.1.6 Displays of Treatment-Emergent Adverse Events Occurred in Multiple Dose Period

Analysis Set:	Safety Analysis Set			
Analysis Variables:	TEAE occurred in multiple dose period			
Categories:	Intensity [Mild, Moderate, Severe]			
Analytical Methods:	The following summaries	will be provided using frequency distribution by dose.		
	TEAEs will be coded using the MedDRA and will be summarized using SOC and PT. SOC			
	will be sorted alphabetically and PT will be sorted in decreasing frequency for tables provided			
	by SOC and PT. SOC and PT will be sorted in decreasing frequency for tables provided by			
	SOC only or PT only.			

- (1) Treatment-Emergent Adverse Events by System Organ Class and Preferred Term
- (2) Treatment-Emergent Adverse Events by System Organ Class
- (3) Treatment-Emergent Adverse Events by Preferred Term
- (4) Drug-Related Treatment-Emergent Adverse Events by System Organ Class and Preferred Term
- (5) Intensity of Treatment-Emergent Adverse Events by System Organ Class and Preferred Term
- (6) Intensity of Drug-Related Treatment-Emergent Adverse Events by System Organ Class, and Preferred Term
- (7) Treatment-Emergent Adverse Events Leading to Study Drug Discontinuation by System Organ Class and Preferred Term
- (8) Serious Treatment-Emergent Adverse Events by System Organ Class and Preferred Term
- (9) QTc prolongation associated Treatment-Emergent Adverse Events by System Organ Class and Preferred Term
- (10) Neurologic Treatment-Emergent Adverse Events by System Organ Class and Preferred Term
- (11) Hyperprolactinemia associated Treatment-Emergent Adverse Events by System Organ Class and Preferred Term
- (12) Drug-Related QTc prolongation associated Treatment-Emergent Adverse Events by System Organ Class and Preferred Term
- (13) Drug-Related Neurologic Treatment-Emergent Adverse Events by System Organ Class and Preferred Term
- (14) Drug-Related Hyperprolactinemia associated Treatment-Emergent Adverse Events by System Organ Class and Preferred Term

The frequency distribution will be provided according to the rules below. Number of subjects

- Summary tables other than (5), and (6)
 A subject with multiple occurrences of TEAE within a SOC will be counted only once in
 that SOC. A subject with multiple occurrences of TEAE within a PT will be counted
 only once in that PT. Percentages will be based on the number of subjects in the safety
 analysis set.
- Summary tables for (5) and (6) A subject with multiple occurrences of TEAE within a SOC or a PT will be counted only once for the TEAE with the maximum intensity. Percentages will be based on the number of subjects in the safety analysis set.

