# 7.8 Subject Replacement

If a subject discontinues from the trial, a replacement subject may be enrolled, if deemed appropriate by the investigator and Sponsor. The investigational site should contact the Sponsor for the replacement subject's medication identification number.

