4.3 Additional Objectives

4.4 Study Design

4.4.1 Trial Design

This is a phase 1, randomized, double-blind, placebo-controlled, single and multiple dose, parallel-group study in up to 3 cohorts of Japanese healthy male subjects, to assess the safety, tolerability, PK, and PD of TAK-906.

Each cohort will consist of 8 subjects where 6 subjects will be randomized to receive TAK-906 and 2 subjects will be randomized to receive matching placebo. The study population will be 24 Japanese healthy male subjects. The randomized subjects will receive a single dose of blinded study drug on Day 1 followed by multiple doses of blinded study drug BID for 5 days from Day 3 to Day 7, except that an evening dose of study drug will not be administered on Day 7. If a subject discontinues from the trial, a replacement subject may be enrolled, if deemed appropriate by the investigator and Sponsor. The investigational site should contact the Sponsor for the replacement subject's medication identification number.

In Cohorts 1 and 2, subjects will be randomized to receive TAK-906 maleate 50 mg, 100 mg, or matching placebo. In Cohort 3, subjects will be randomized to receive TAK-906 maleate 10 mg, or matching placebo. For each cohort, follow-up assessments will occur on Day 14 which is 7 days

TAK-906-1004	Page 9 of 33
Statistical Analysis Plan	10 Nov 2017

after completion of the last treatment dose. Dose escalation to Cohort 2 will be based on a full blinded review of safety and tolerability data until follow-up assessments from Cohort 1. Cohort 3 will be conducted in parallel with Cohort 1 or 2. Dose level in Cohort 2 may be changed within the range up to 100 mg, as appropriate, based on safety and pharmacokinetic data in preceding cohorts, ie, 50 mg BID in Cohort 1 or 10 mg BID in Cohort 3 (if applicable) of this study; however, no higher dose than the proposed highest dose (100 mg BID).

(IRB) approval to revise the study protocol.

The planned dose levels of TAK-906 to be evaluated are outlined in Table 1.

Cohort (a)	TAK-906 malesate Dose (a, b, c)		Subjects
Conort (a)	Single Dose Period	Multiple Dose Period (d)	Subjects
1	50 mg single dose	50 mg BID for 5 days	6 TAK-906
	on Day 1	from Days 3 to 7	2 Placebo
2	100 mg single dose	100 mg BID for 5 days	6 TAK-906
	on Day 1	from Days 3 to 7	2 Placebo
3	10 mg single dose	10 mg BID for 5 days	6 TAK-906
	on Day 1	from Days 3 to 7	2 Placebo

Table 1Summary of Dose Cohorts

BID=twice daily

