7.0 METHODS OF ANALYSIS AND PRESENTATION

7.1 General Principles

7.1.1 Study Definitions

The following definitions and calculation formulas will be used.

- TEAE: An AE whose date of onset occurs on or after the start of study drug. A TEAE whose relationship to study drug is missing will be considered drug-related. A TEAE whose intensity is missing will be considered severe.
- PTE: An AE whose date of onset occurs before the start of study drug..
- Descriptive statistics: number of subjects with non-missing values, mean, standard deviation, maximum, minimum, and quartiles, including geo-mean, geo-CV as needed
- QTcF interval (msec): QT interval (msec) / (RR interval (msec)/1000)^{0.33} (rounded to the nearest whole number)
- Baseline values: The last evaluable observation (ie, non-missing) before the first dose of study drug. If no evaluable observation is obtained before the first dose, the baseline value will be missing.
- TEAE occurred in single dose period: A TEAE occurred prior to start of multiple dosing.
- TEAE occurred in multiple dose period: A TEAE occurred from Day 3 postdose through Day 14 (follow-up visit).

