7.2 Analysis Sets

The Safety Analysis Set will be defined as all subjects who received at least one dose of the study drug.

The PK Analysis Set will consist of subjects who received at least one dose of the study drug, completed the minimum protocol specified procedures with no significant protocol deviations which are listed below, and were evaluable for the pharmacokinetics.

- Subjects who did not meet inclusion criteria #3or #4
- Subjects who met exclusion criteria #1, #4, #5, #6, #7, #9, #10, #12, #13, #15, #17, #18, #19, #23 or #25

The PD Analysis Set will consist of subjects who received at least one dose of the study drug, completed the minimum protocol specified procedures with no significant protocol deviations which are listed below, and were evaluable for the pharmacodynamics.

- Subjects who did not meet inclusion criteria #3or #4
- Subjects who met exclusion criteria #1, #4, #5, #6, #7, #9, #10, #12, #13, #15, #17, #18, #19, #23 or #25

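### Multiple-dose-period TEAE percentages use every treated subject as denominator, so anyone who leaves before the first Day 3 dose dilutes repeat-dose incidence

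*SAP*

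**What the plan says.** **Denominator.** For the multiple-dose-period displays, SAP 7.11.1.6 says: "Percentages will be based on the number of subjects in the safety analysis set". The sentence is given twice, once for intensity tables (5) and (6) and once for the rest, so it governs all 14 tables.

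**Membership of that set.** SAP 7.2: "The Safety Analysis Set will be defined as all subjects who received at least one dose of the study drug". The Day 1 dose alone qualifies.

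**Numerator.** SAP 7.1.1 defines a multiple-dose-period event as follows: "A TEAE occurred from Day 3 postdose through Day 14 (follow-up visit"). Its counterpart reads: "TEAE occurred in single dose period: A TEAE occurred prior to start of multiple dosing".

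**Dosing.** SAP 4.4.1 gives each subject "a single dose of blinded study drug on Day 1 followed by multiple doses of blinded study drug BID for 5 days from Day 3" onward. Nothing is dosed on Day 2, so a treated subject can leave before repeat dosing begins.

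**Replacement.** Protocol 7.8: "If a subject discontinues from the trial, a replacement subject may be enrolled". This is at the discretion of the investigator and Sponsor. Nothing removes the withdrawn subject from the Safety Analysis Set.

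**Overview table.** SAP 7.11.1.3 names the Safety Analysis Set and asks for percentages, but states no denominator rule.

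**The concern.** A period-specific incidence should be divided by the people who entered the period. Here the numerator starts with the Day 3 dose and the denominator with the Day 1 dose. A subject who drops out in between adds to the denominator of a repeat-dose table without having had a repeat dose. With six subjects planned per active dose, each such subject matters.

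Early leaving is possible under the plan. ECGs run to 24 hours after the single dose, laboratory tests and a physical examination fall on Day 2, and Protocol 7.6 lists findings that lead to discontinuation.

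The planned output would not reveal the mismatch directly. SAP 7.7 (exposure) is marked not applicable, and SAP 7.3.4 reports discontinuations by dose and reason but not by time. No planned table gives the number who started Day 3 dosing.

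At stake is how the stand-alone repeat-dose tolerability percentages are read, in a trial whose primary endpoint is safety and tolerability.

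**Working it through.** **Planned group sizes.** SAP 4.4.1 and 6.0 give three cohorts of 6 active and 2 placebo: 3 × (6 + 2) = 24, which matches the stated total. Each active dose has 6 subjects. Pooled placebo has 3 × 2 = 6. The documents state no TEAE percentage and no power figure to reproduce.

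**Notation.** N is the number in the Safety Analysis Set at a dose, d the number who leave after Day 1 dosing but before the first Day 3 dose, and x the number of repeat-dosed subjects with an event.

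- SAP percentage = x / N
- At-risk percentage = x / (N − d)
- Ratio of SAP to at-risk = (N − d) / N

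The documents give no value for d, so 0, 1 and 2 are assumed. With replacement in the same arm, N = 6 + d.

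| Case | N | N − d | Ratio | x = 1: SAP vs at-risk | x = 2: SAP vs at-risk |
|---|---|---|---|---|---|
| d = 0 | 6 | 6 | 1.000 | 16.7% vs 16.7% | 33.3% vs 33.3% |
| d = 1, not replaced | 6 | 5 | 0.833 | 16.7% vs 20.0% | 33.3% vs 40.0% |
| d = 2, not replaced | 6 | 4 | 0.667 | 16.7% vs 25.0% | 33.3% vs 50.0% |
| d = 1, replaced | 7 | 6 | 0.857 | 14.3% vs 16.7% | 28.6% vs 33.3% |
| d = 2, replaced | 8 | 6 | 0.750 | 12.5% vs 16.7% | 25.0% vs 33.3% |

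One leaver and one affected subject give a gap of 3.3 points without replacement and 2.4 points with it.

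**How likely is d ≥ 1?** If each subject independently leaves before Day 3 with probability q, the chance of at least one leaver is 1 − (1 − q)^n. For q = 2%, 5% and 10% (assumed, not from the documents), this is 11%, 26% and 47% in one group of 6, and 38%, 71% and 92% among all 24.

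**Dependence on period assignment.** The table assumes that a leaver's own later events stay out of the numerator. That follows if, for someone who never starts multiple dosing, every event counts as preceding it. SAP 7.1.1 does not say so, and AE collection runs to Day 14 (Protocol 10.2.9.1). If period were assigned by calendar day, a leaver's Day 6 event would enter the numerator. With d = 1, no replacement, and one event among the five repeat-dosed subjects, the SAP figure would be (1 + 1)/6 = 33.3% against an at-risk 1/5 = 20.0%, an overstatement.

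**The case against.** The best case for leaving the rule alone has four parts.

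1. **The condition may never occur.** The window is about 48 hours, in confinement, in healthy volunteers, and no dropout rate is given. This stands: with no early leaver the effect is zero.

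2. **Nothing important rests on these percentages.** Protocol 11.1.5.1 plans TEAE summaries for the single dose period and for both periods combined, and the full Safety Analysis Set suits both. The stand-alone multiple-dose table is an SAP addition. Cohort 2 entry rests on blinded review of the safety data (Protocol 6.2), the trial stopping criteria count subjects (Protocol 6.5.4.1), no between-group test of TEAEs is planned, and all TEAEs are listed. At this size the estimates are imprecise anyway: exact 95% intervals are about 0.4–64% for 1/6 and 0.5–72% for 1/5. This also stands, and it limits the priority.

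3. **A constant denominator is defensible.** It is pre-specified, it is the same across the three sets of tables, and it avoids conditioning on having tolerated Day 1. That is fair, but SAP 7.11.1.4 already gives the all-treated view. A table labelled as multiple dose period will be read as incidence under repeat dosing.

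4. **The seven-subject case rests on an assumption.** Replacement is discretionary, and Protocol 9.1.1.2 says only that a different medication number is used, without naming the arm. The 1/7 figure therefore holds only for replacement in the same arm.

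A reader might go further and infer that the error always understates incidence, or that it would be worst at a high active dose. The documents support neither. The direction depends on the unsettled period assignment shown in the working. No figure links early leaving to dose, and Protocol 6.3.2 describes 100 mg BID as well tolerated in non-Japanese subjects.

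**Conclusion.** The point holds as a conditional one. SAP 7.11.1.6 states a denominator that does not match its numerator, and no other section restricts it. If a leaver's events are kept in the single dose period, one early leaver among six scales the reported repeat-dose incidence by 0.833, or by 0.857 if he is replaced in the same arm; with none the factor is 1.

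It would be wrong to infer that the trial's safety conclusions or dose escalation are compromised: the counts, listings, overall tables and single-dose tables remain correct. It would also be wrong to say that SAP 7.11.1.3 states a faulty rule; it states none and needs only a clarification. Priority: minor.

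**What to change.** Three sentences in the SAP:

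1. **SAP 7.11.1.6:** base percentages on Safety Analysis Set subjects who received at least one dose of study drug on or after Day 3, and show that N in each column header.
2. **SAP 7.11.1.3:** state the same denominator.
3. **SAP 7.1.1:** assign TEAEs in subjects who never started multiple dosing to the single dose period, whatever the calendar day. Without this, a subject could be in the numerator but not in the new denominator.

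Keep the full Safety Analysis Set for the overall and single-dose tables. The cost is one population flag and a column-header N in programming. No data collection or protocol amendment is needed. Settling it in advance avoids a choice of denominator after an early withdrawal has been seen.
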